### 7.2. Discontinuation of Study Intervention

HTD1801 treatment must be discontinued for a subject if any of the following criteria are met.

- Adverse event that may jeopardize subject's safety
- Grade 3 and above adverse events (AEs) for which the causality is considered as related to investigational agent
- Discontinuation due to drug-induced liver injury (refer to Section 10)
- Request by the subject
- Pregnancy

For subjects who discontinue investigational study drug, an Early Termination Visit should be conducted at the time the investigational study drug is discontinued (see Section 7.3). Subjects who terminate from the study prior to Study Visit Week 12 will be requested to return to the clinic 28 days **after the date of last dose** of investigational study drug and complete the equivalent of the Week 16 follow up visit assessments. If necessary, arrangements can be made with the site and the subject to conduct the visit virtually and make use of a local laboratory for the study required Study Visit Week 16 lab tests.

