#### **9.2.6. Safety Related Laboratory Assessments**

A central laboratory will be utilized to perform safety related clinical laboratory assessments as specified in the Schedule of Activities [Table 1](#) and as described below in [Table 3](#). Samples for laboratory assessments performed at Baseline must be collected prior to study drug dosing. The Investigator or qualified designee must review the results of all central laboratory testing to assess subject eligibility at Screening and Baseline, as well as continued study participation for the duration of the study. Procedures for sample collection and handling will be detailed in the central laboratory manual and/or Study Procedures Manual (SPM).

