**Table 5 Assessment of Causality of AEs**

Term	Definition
Possibly related	The AE may be related to the investigational agent(s) or intervention: the AE has a temporal relationship to the administration of the investigational agent(s) or research intervention.
Unrelated (or not related)	The AE is clearly not related to the investigational agent(s) or intervention: the AE has no temporal relationship to the administration of the investigational agent(s) or research intervention, and follows no known or suspected pattern of response, and an alternative cause is present.

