## **10. DRUG-INDUCED LIVER INJURY (DILI) MONITORING AND STOPPING RULES**

It is important for study staff to monitor subjects for drug-induced liver injury and to educate subjects to recognize DILI symptoms and seek immediate medical attention.

Liver enzymes and serum bilirubin levels will be assessed at each clinic visit. Elevated ALTs will be assessed and dealt with as shown in [Table 7](#) and [Table 8](#). There are separate DILI monitoring plans based on whether the subject had normal or near normal versus elevated ALT values at baseline, because some subjects with PBC may have normal or near normal ALT levels at baseline. The Medpace Reference Laboratory (MRL) which will serve as the central laboratory for this study has defined its upper limit of normal for ALT as 53 U/L, in both males and females. The study therefore considers up to 60 U/L as being normal or near normal while >60 U/L is considered elevated.

Persistent Cholestatic liver injury is characterized by elevations in serum alkaline phosphatase and/or bilirubin (see [Table 7](#) and [Table 8](#)).

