#### **10.1.2. Detection of Potential DILI in Subjects with Elevated ALT levels at baseline**

Because subjects to be enrolled in the study have underlying liver disease, it is very likely that they may have an elevated ALT level at baseline and therefore multiples of the baseline will be used for DILI monitoring where the baseline value is elevated. The baseline ALT value will be calculated as the average of those obtained at the screening and baseline visits. An on-treatment ALT value more than 3x the baseline value will be the threshold for triggering the DILI monitoring plan for these subjects.

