Elevated Liver Function Tests Worsen or Clinical Symptoms Develop	If ALT is $> 8$ x ULN of baseline on one occasion, or If ALT is $> 5$ x ULN of baseline for more than 2 weeks, or If ALT is $> 3$ x ULN of baseline AND bilirubin is $> 2$ X ULN OR INR $> 1.5$ , or	

Permanently STOP investigational study drug

Continue monitoring until all abnormalities return to normal or to the baseline state

All DILI monitoring results must be recorded in the DILI monitoring eCRF

	If ALT is >3x ULN of baseline AND subject is symptomatic (severe fatigue, nausea, vomiting, right upper quadrant pain or tenderness, fever, rash, and/or eosinophilia (>5%))	
Persistent Cholestatic Liver Injury	If serum ALP is >2x ULN and total and direct bilirubin is >2x ULN	

• Permanently STOP investigational study drug

• Continue monitoring until all abnormalities return to normal or to the baseline state

• All DILI monitoring results must be recorded in the DILI monitoring eCRF

\* The PI must review the local lab results promptly. Local lab results must be entered into an unscheduled visit within the EDC

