### 12.2. Sample Size Determination

A sample size of 30 subjects provides  $\geq 90\%$  power for the primary endpoint assuming a mean percent reduction in ALP of 15% and a SD of 25%. Power calculations use a 5% one sided alpha and a t-test. Sample size calculation were performed in PASS ([PASS 2014](#)).

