#### **12.4.6. Baseline Descriptive Statistics**

Subjects who discontinue treatment or withdraw from the study, and the reasons for doing so, will be summarized. Subject demographic and baseline characteristics will be summarized.

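### Tables 7 and 8 give no bilirubin stop to a subject with ALP at or below 2x ULN, no ALT >3x limb met and INR not >1.5; the SAP liver-threshold outputs count ALT only

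*Protocol*

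**What the plan says.** **Stops in the tables.** Table 7 (baseline ALT up to 60 U/L) and Table 8 (above 60 U/L) carry the same cholestatic row: "If serum ALP is >2x ULN and total and direct bilirubin is >2x ULN". Elsewhere in the tables bilirubin appears in one stop limb, which pairs ALT >3x with bilirubin >2x ULN or INR >1.5. The remaining limbs (ALT >8x once, ALT >5x for over two weeks, ALT >3x with symptoms) do not use bilirubin.

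**Text of Section 10.** The introduction says "Persistent Cholestatic liver injury is characterized by elevations in serum alkaline phosphatase and/or bilirubin" and points to the tables, which join the conditions with *and*.

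**Monitoring trigger.** It is defined by ALT. For elevated baselines, Section 10.1.2 says "An on-treatment ALT value more than 3x the baseline value will be the threshold for triggering the DILI monitoring plan"; Section 10.1.1 uses 3x ULN for the others. Under Section 10.1.3, values reaching a threshold in Tables 7 and 8 are flagged to the medical monitor.

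**Stops outside the tables.** Section 7.2 requires discontinuation for an adverse event that could endanger the subject, and for "Grade 3 and above adverse events (AEs) for which the causality is considered as related to investigational agent". Section 9.2.6 has the investigator review central laboratory results for eligibility "as well as continued study participation for the duration of the study".

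**SAP.** Section 2.3 defines the liver monitoring threshold by ALT alone. Section 3.4.3 summarizes the proportion crossing it and lists ALT values for those subjects.

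**The concern.** The one table rule aimed at cholestatic injury depends on a marker that the drug is meant to lower. A subject who enters with ALP between 1.5 and 2x ULN, or whose ALP falls below 2x ULN on treatment, is outside that row whatever bilirubin does, unless ALP rises above the cut. If ALT also stays low, neither a numeric stop nor the medical-monitor flag is reached. Whether drug is stopped then depends on how the event is recorded, graded or judged.

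The second consequence is in reporting. The planned liver-threshold summary could show no crossings although a subject had met the cholestatic stop row or had bilirubin well above 2x ULN. In a liver-disease trial, a reader would expect that table to show such a case.

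**Working it through.** **Inputs.** ALP ULN 116 U/L (SAP 2.3.1). Total bilirubin ULN 1.21 mg/dL and ALT ULN 53 U/L (SAP 2.3.2). Entry ALP at least 1.5x ULN (Protocol 5.1). Total bilirubin entry cap 1.3 mg/dL outside Gilbert's Syndrome (Protocol 5.2). The direct bilirubin ULN is not given, and local laboratory ranges may differ.

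**The plan's own figure.** The 180 U/L that Section 10.1.1 and the tables give as 3x ULN is 3 × 60, using the near-normal limit. On the laboratory ULN it would be 3 × 53 = 159 U/L. Both are carried below.

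**Thresholds on the central range.**
- Entry floor: 1.5 × 116 = 174 U/L.
- ALP limb of the cholestatic row: above 2 × 116 = 232 U/L.
- Total bilirubin limb: above 2 × 1.21 = 2.42 mg/dL, which is 2.42 / 1.3 = 1.86 times the entry cap.

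**Logic.** Fix total bilirubin >2x ULN, ALP at or below 2x ULN and ALT not >3x. The 5x and 8x ALT limbs are then false as well. Direct bilirubin, INR and symptoms remain free, giving 2 × 2 × 2 = 8 combinations. The limb with INR can be read in two ways:

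| Reading | Combinations that stop | Combinations that do not |
|---|---|---|
| ALT >3x and (bilirubin >2x or INR >1.5) | 0 | 8 |
| (ALT >3x and bilirubin >2x) or INR >1.5 | 4, all through INR | 4 |

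So if INR is not above 1.5, no combination stops under either reading. Table 1 does not schedule INR at Weeks 2, 4 or 8.

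**Can a subject get there?** Entry at 174 to 232 U/L already lies at or below the ALP cut. Section 12.2 sizes the study "assuming a mean percent reduction in ALP of 15% and a SD of 25" percent. A fall of exactly 15% brings a baseline of up to 2 / 0.85 = 2.35x ULN, or 232 / 0.85 = 273 U/L, to or below the cut. This shows only that the region is reachable.

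**Example.** ALP 225 U/L (225 / 116 = 1.94x ULN), total bilirubin 5.0 mg/dL (5.0 / 1.21 = 4.13x ULN) with direct bilirubin also >2x ULN, ALT 100 U/L (100 / 53 = 1.89x ULN), INR not above 1.5.
- Cholestatic row: fails on ALP (225 is not above 232).
- Table 7 ALT limbs: 100 is below both 159 and 180, so none is met if the limb means 3x ULN. The cell also mentions baseline. If read as 3x the subject's own baseline, a baseline below 100 / 3 = 33.3 U/L would meet the bilirubin limb; starting at 30 U/L, for instance, the limit is 90. Section 10.1.1 favours the ULN reading.
- Table 8 ALT limbs: baseline exceeds 60, so 3x baseline exceeds 180 and ALT 100 does not reach it. A subject starting at ALT 100 would have to exceed 300 U/L.

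On the ULN reading of Table 7, the example meets no stop row in either table.

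**SAP outputs compared.**
- Threshold proportion and listing (2.3, 3.4.3): ALT only. A subject meeting the ALT-plus-bilirubin limb appears through ALT, with no bilirubin breakdown.
- Out-of-range tables (3.4.3): based on the normal range, so 1.3 and 5.0 mg/dL both count simply as high.
- By-visit bilirubin summaries (2.5.2, 3.3.2, with maxima under 3.1): would show a peak used for a visit window. Section 2.4 keeps only the result closest to the target day, so an unscheduled peak can drop out.
- Counts of subjects meeting the cholestatic row, or with high bilirubin outside it: none planned.

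**The case against.** The strongest reply is that mandatory stops already cover the case. Abnormal laboratory findings can be adverse events (9.3.1), severity follows CTCAE v5.0, and Section 7.2 obliges discontinuation for related Grade 3+ events or events that endanger the subject. Table 5 has only two causality levels. To be called unrelated, an event must lack a temporal relationship and must be one that "follows no known or suspected pattern of response, and an alternative cause is present", so an unexplained rise on drug would be possibly related. Liver tests are assessed at each visit and the investigator reviews them.

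This largely stands. A reader might infer that the example subject would be left on drug; the documents do not support that. They do not reproduce the CTCAE bilirubin cut-offs, so it cannot be said that the example escapes Section 7.2. What remains is that these routes set no bilirubin limit in the protocol. They also require the rise to be treated as an adverse event in the first place, while Section 9.3.1 excludes expected disease progression and Section 4.2 expects markers to worsen over time.

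A reader might also apply the planning mean and SD to ALP and present the result as the share of subjects left unprotected. That would be a marginal chance of ALP falling below the cut. The gap also needs both bilirubins to rise and ALT to stay low, and a subject developing cholestatic injury need not follow the average ALP course.

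On the SAP, bilirubin is not unreported. Summaries with maxima and a clinical laboratory listing exist, discontinuations are covered by "Subjects who discontinue treatment or withdraw from the study, and the reasons for doing so, will be summarized", and TEAEs leading to discontinuation are listed. With about 30 subjects, individual values could be found. The ALT-only definition also follows the protocol's own trigger. The SAP part is therefore secondary. The *and/or* sentence in Section 10 is descriptive and is no competing rule.

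**Conclusion.** The point holds as a minor gap in the table rules. With ALP at or below 2x ULN, no ALT >3x limb met and INR not above 1.5, no bilirubin value triggers a stop in Tables 7 or 8. With no ALT threshold met, none triggers the Section 10.1.3 flag. The gap can be present from entry and can open as ALP falls. It does not mean that the protocol lacks any safeguard for bilirubin.

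No frequency is claimed: the documents give neither a baseline ALP distribution nor an expected rate of bilirubin rise. The figures rest on the central ranges in the SAP, and the example rests on INR not above 1.5 and the ULN reading of Table 7. Sample size, endpoints and the primary analysis method are unaffected.

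**What to change.** 1. **Tables 7 and 8.** Keep the existing cholestatic row as an immediate stop. Add a row limited to ALP at or below 2x ULN: total and direct bilirubin both >2x ULN triggers a medical-monitor flag and a repeat panel within 2 to 5 days (the interval already used for ALT), with a permanent stop if confirmed. Limiting the row by ALP avoids two conflicting instructions for one subject. Requiring direct bilirubin protects subjects with Gilbert's Syndrome. Align the *and/or* sentence in Section 10 at the same time.
2. **SAP 2.3 and 3.4.3 (secondary).** Add to the threshold summary and listing the number of subjects with any post-baseline result, including unscheduled ones, that meets the cholestatic row, the new row, or ALT >3x with bilirubin >2x ULN.

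**Cost.** A short protocol clarification, one extra table and a longer listing, an occasional repeat draw, and possibly a rare extra discontinuation. Total and direct bilirubin are already in the chemistry panel drawn at every scheduled post-baseline visit.

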**Table 8: Liver Monitoring Procedure – For Subjects with Calculated Baseline ALT >60 U/L (Elevated ALT)**

Event	Observation	Action
ALT becomes elevated	Isolated increase in ALT to $\geq 3$ x ULN (i.e., $\geq 180$ u/L) with no increase in serum bilirubin and presence of symptoms of anorexia, nausea, fatigue, right upper abdominal discomfort or vomiting preceding or following the isolated increase in ALT to $>3$ x ULN.	
 
Promptly repeat serum chemistry panel (ALT, AST, ALP, total bilirubin and direct bilirubin) within 2 to 5 days* 
 
If subject lives remotely from the site, local labs may be obtained
 
The PI must review the local lab results promptly and local lab results must be entered into an unscheduled visit within the EDC
 
Continue investigational study drug
 
 
 

ALT remains elevated	If ALT remains $\geq 3$ x calculated baseline	
 
Obtain serum chemistry panel (as above) and repeat 2 – 3 x/week until stable
 
Frequency of testing can be decreased to once per week or less if abnormalities stabilize or the subject is asymptomatic
 
Obtain detailed history of symptoms and prior or concurrent medical history
 
Obtain history of concomitant drug use including non-prescription medications, herbal & dietary preparations, alcohol use, recreational drug use, and special diets.
 
Where appropriate, rule out acute viral hepatitis types A, B, C, D, & E, autoimmune or alcoholic hepatitis, NASH, hypoxic/ischemic hepatopathy & biliary tract disease
 
Obtain a history of exposure to environmental chemical agents
 
Obtain additional tests to evaluate liver function, as appropriate (e.g., INR, CBC with differential)
 
Continue investigational study drug
 

ALT decreases	ALT return to $<3$ x ULN or baseline level	
 
Resume study-required laboratory assessments as per the Summary of Events table and continue investigational study drug
 

Elevated Liver Function Tests Worsen	If ALT is $>8$ x ULN of calculated baseline on one occasion, or If ALT is $>5$ x ULN of calculated baseline for more than 2 weeks, or If ALT is $>3$ x ULN of calculated baseline AND bilirubin is $>2$ X ULN OR INR $>1.5$ , or	
 
Permanently STOP investigational study drug
 
Continue monitoring until all abnormalities return to normal or to the calculated baseline state
 
All DILI monitoring results must be recorded in the DILI monitoring eCRF
 

	If ALT is >3x ULN of calculated baseline AND subject is symptomatic (severe fatigue, nausea, vomiting, right upper quadrant pain or tenderness, fever, rash, and/or eosinophilia (>5%))	
Persistent Cholestatic Liver Injury	If serum ALP is >2x ULN and total and direct bilirubin is >2x ULN	

• Permanently STOP investigational study drug

• Continue monitoring until all abnormalities return to normal or to the calculated baseline state

• All DILI monitoring results must be recorded in the DILI monitoring eCRF

\* The PI must review the local lab results promptly. Local lab results must be entered into an unscheduled visit within the EDC

## **11. COVID-19 PANDEMIC CONTINGENCIES**

### **11.1. Potential Impact of COVID-19 on Study Conduct**

The potential impact from quarantine restrictions, site closures and travel restrictions may limit the site's and subject's capability to have on-site visits.

### **11.2. Operational Contingencies related to COVID-19 Pandemic**

Local site policies and process for COVID-19 monitoring, for example, temperature check, COVID-19 exposure history, recent travel history and use of personal protective equipment must be followed.

The study protocol specifies that all visits are in-clinic visits but allows for contingency measures for Study Visits Week 2, 4, 8, 16 and the Early Termination visit in the occurrence where a subject is unwilling or unable to participate in an in-clinic visit due to the COVID-19 pandemic.

In that instance, the site will work with the study subject to obtain study-required blood draws at a local laboratory or arrangements will be made to have the home health provider obtain the visit specific blood draw for the study-required laboratory assessments.

Other visit assessments will have to occur via a remote visit by telephone or a video conference, per site practice and procedures, to assess changes in the subjects' health condition, make note of any changes in concomitant medications, and inquire about adverse events. The visit must be documented as a telephone/video conference visit with arrangements for laboratory assessments.

The site will enter the laboratory results, if obtained at a local laboratory, into the EDC as an "unscheduled" visit that will be mapped to the specific visit for which local laboratory data were obtained. If the visit specific blood draw is obtained by the home health service provider, it will be shipped to the central laboratory; the results will be entered into the central laboratory database and merged with the clinical database at the completion of the study.

Every effort must be made to complete the full scope of the study visit activities and procedures. Any deviation from the procedures and protocol-specified contingency measures due to COVID-19 must be clearly documented as COVID-19-related and reported to the IRB as applicable.

The PI and study personnel are responsible for ensuring full investigational product accountability.

## 12. STATISTICAL CONSIDERATIONS

### 12.1. Statistical Hypotheses

The primary hypothesis for this study is that treatment with HTD1801 results in reductions in ALP:

$$H_0: \frac{ALP_{Week\ 12} - ALP_{Baseline}}{ALP_{Baseline}} \geq 0 \text{ vs. } H_a: \frac{ALP_{Week\ 12} - ALP_{Baseline}}{ALP_{Baseline}} < 0$$

The estimand will be the percent change from baseline and will be measured within all subjects on treatment and who provide data at Week 12. This estimand is similar to the While on Treatment Strategy outlined in ICH e9 R1 but is limited to on treatment results at Week 12 (i.e., results from prior to Week 12 are not included in the analysis of the Week 12 results).

Testing will be one sided using a 5% alpha level.

### 12.2. Sample Size Determination

A sample size of 30 subjects provides  $\geq 90\%$  power for the primary endpoint assuming a mean percent reduction in ALP of 15% and a SD of 25%. Power calculations use a 5% one sided alpha and a t-test. Sample size calculation were performed in PASS ([PASS 2014](#)).

### 12.3. Populations for Analyses

The following analysis populations will be defined for statistical analysis:

- Screened population
  - The Screened population will consist of all subjects who sign the study informed consent.
- Intention-to-treat (ITT) population
  - The ITT population will consist of all subjects that receive at least one dose of HTD1801. This population will be used for all efficacy, safety, and baseline/demographic analyses and summaries.
- Population undergoing pharmacokinetic testing
  - At least 6 subjects will undergo sparse PK sampling at weeks 6 and 12.

### 12.4. Statistical Analyses

#### 12.4.1. General Approach

Endpoints will be summarized using descriptive statistics. For continuous variables n (number of subjects with data), mean, standard deviation, median, minimum, and maximum will be used. For categorical results the number of subjects and the percent of subjects per category will be summarized. Confidence intervals will be generally reported using 95% two-sided confidence intervals. When testing is used p-values with four decimal places will be reported; no adjustment for multiplicity will be conducted.

Missing data will not be imputed for the efficacy analyses. Missing dates for adverse events and concomitant medication will be imputed to allow these items to be summarized as on or off treatment.

#### **12.4.2. Analysis of the Primary Efficacy Endpoint(s)**

Alkaline phosphatase levels, change from baseline, and percent change from baseline will be summarized with descriptive statistics and 95% normal approximation confidence intervals. Testing for the percent change endpoint using a t-test will also be performed. Given the limited sample size (i.e. less than 30 subjects) and the potential for right skewed data the normality assumption may not be fully accurate. Hence, the true alpha level may theoretically not be 5%. As such, these tests will be considered descriptive more than confirmatory.

#### **12.4.3. Analysis of the Secondary Endpoint(s)**

The secondary endpoints including the secondary ALP endpoints will be summarized using descriptive statistics. Summary statistics at each timepoint that data is captured will be provided for the result as well as the change from baseline, when change from baseline is applicable. Confidence intervals will be produced for changes in serum bilirubin and change in gamma-glutamyl transferase.

